Final Visit: Subjects that participated in titration visits will return to the clinic for the final visit 4 weeks after the neural fulcrum was achieved. Autonomic testing and/or cardiopulmonary exercise testing will be performed. The study neurologist will work with the patient to decide if they can do all of the testing or some of the testing. The final visit will take up to 3 hours.

Subjects will be monitored for changes in seizure frequency or duration at each clinic visit as well as any adverse events during the study by having continuous 24 hours per day/7 days per week access to the study team with the neurologist on call.

C. STUDY DURATION

Subjects will be in the study up to 9 weeks. All subjects will undergo baseline autonomic testing and/or cardiopulmonary exercise. Subjects that complete the baseline only testing will complete the study in one visit. Subjects that participate in titration visits will have VNS titration over a 2-4 week period. After titration is complete, the IPG's will be programmed to the neural fulcrum stimulation protocol and left there for 4 weeks. Following the 4 week phase, the autonomic testing and/or cardiopulmonary exercise test will be repeated.

D. Procedures to assess efficacy

Autonomic Testing

- **Valsalva Maneuver:** Improvements in late phase II and in phase IV of the Valsalva maneuver, and a normalized pressure recovery time (PRT) after up-titrated VNS. Poor adrenergic response is indexed by a prolonged PRT, absent or blunted phase IV or late phase II. A 10% improvement in these parameters in response to up-titrated VNS will be considered a significant clinical benefit.
- **Tilt Test:** (orthostatic stress) A 10% decrease in tilt-induced hypotension or a 10% decrease in the heart rate response to a 70 degree heads up tilt after up-titration of VNS will be considered a significant clinical benefit.
- **Oximetry**
- **Electrocardiogram:** The ECG will be used to assess Tp-Te (a measure of repolarization heterogeneity in the heart).

- **Cold Pressor Test:** A 10% reduction in evoked heart rate (HR) and blood pressure (BP) response to cold stimulus is considered a significant response of clinical benefit.

Cardiopulmonary Testing

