This is a progressive dynamic exercise test. A 10% improvement in exercise duration and/or a 10% improvement heart rate recovery after exercise will be considered a significant clinical benefit. Heart rate and blood pressure will also be plotted against time. At 85% of the maximum exercise achieved before up-titration of VNS a 5% decrease in heart rate at the same intensity point will be considered a significant clinical benefit with VNS.

E. Procedures to assess safety

- Incidence of adverse events

F. Schedule of study visits

- Please see Schedule of Events in Appendix 1

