8. ADVERSE EVENTS

A. DEFINITION OF ADVERSE EVENT

An adverse event (AE) is any unfavorable and unintended sign (including an abnormal laboratory finding), symptom, or disease temporally associated with the use of a medical treatment or procedure regardless of whether it is considered related to the medical treatment or procedure (attribution of unrelated, unlikely, possible, probable, or definite).

All Adverse Events (AE) will have the following assessed by the study team, as defined below:

- Diagnosis
- Event description
- Dates of onset and resolution
- Causality: assessment of relatedness to procedure
- Severity
- Outcome

B. ADVERSE EVENTS MONITORING

The patient's status will be closely monitored by the study team to assess adverse events. The study team that includes neurosurgery, neurology, and electrophysiology, will be conducting the study protocol and are the primary care team for the patient.

C. ADVERSE EVENTS

All reported AEs will be monitored by the study team until they are adequately resolved or explained.

Potential Adverse Events

Most common adverse events seen in long-term treatment with VNS (12mo and 5yrs) as reported in the literature. These symptoms were rated as mild-moderate and did not require adjustment of parameters:

- Voice alteration 55/18.7%
- Headache 16%
- Cough 15/1.5%
- Pain 15/4.7%
- Paresthesia (abnormal skin sensation) 15/1.5%
- Dyspnea 13/12.3%
- Pharyngitis 10%
- Depression 5%
- Infection 6%

Increase in seizure frequency is also a potential adverse event and will be discussed with patients during screening.

D. SERIOUS ADVERSE EVENTS

- An event that is fatal, resulting in death
- An event that is life threatening. In the opinion of the study center physician, the patient was at immediate risk of death due to the event as it occurred;
- An event that results in persistent or significant disability/incapacity;
- An event that requires inpatient hospitalization or prolongs hospitalization;
- An important medical event that, based upon appropriate medical judgment, may jeopardize the patient and may require medical or surgical intervention to prevent one of the outcomes listed above.

NOTE: Prolonged hospitalizations for a pre-existing condition is not considered a serious adverse event.

E. REPORTING SERIOUS ADVERSE EVENTS

The site investigator is responsible for ensuring that all SAEs are fully recorded and reported to the IRB per IRB reporting requirements.

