10. DATA HANDLING

The patient will be assigned a study number after the consent is signed and the patient is enrolled. Study data will be collected and stored using the study code. Personally, identifiable data will not be collected, transmitted, or stored via the internet. A secure network server will be used to store data. A study code will link the data to the study subject. A key to the code exists. Only the study team members listed in the IRB will have access to the code.

This is a safety and feasibility study, therefore the data will be maintained for future research in the case that:

- The study team wants to use the data set to investigate any additional research questions.
- The study team uses the data set as part of a larger study in the future.

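### Tp-Te, the Valsalva phases and pressure recovery time are not masked to visit or device state, so reader expectation can enter their before/after differences

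*Combined protocol and SAP*

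**What the plan says.** Section 5.D (Procedures to assess efficacy) names the measures. For the ECG: "The ECG will be used to assess Tp-Te (a measure of repolarization heterogeneity in the heart". It gives no lead, beat selection, T-wave-end method, reader, benefit threshold or direction of benefit for Tp-Te. For the Valsalva maneuver it looks for "Improvements in late phase II and in phase IV of the Valsalva maneuver, and a normalized pressure recovery time (PRT) after up-titrated VNS". It describes an abnormal trace in words: "Poor adrenergic response is indexed by a prolonged PRT, absent or blunted phase IV or late phase II". The benefit rule for the Valsalva measures is "A 10% improvement in these parameters in response to up-titrated VNS will be considered a significant clinical benefit".

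The exercise measures have their own rules: "A 10% improvement in exercise duration and/or a 10% improvement heart rate recovery after exercise will be considered a significant clinical benefit", and at a fixed workload "a 5% decrease in heart rate at the same intensity point will be considered a significant clinical benefit with VNS".

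Section 6 compares baseline with stimulation by paired t test in 12 subjects, each serving as their own control, and calls the study primarily exploratory. Section 5.B allows the device to be either off or on during testing.

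On who does the work, Section 8.B says that the study team "will be conducting the study protocol and are the primary care team for the patient". The separate physician group in Section 9 reviews the protocol, data and safety twice a year and is given no endpoint reading. Section 10 says "Study data will be collected and stored using the study code". That code identifies the subject; nothing says that it conceals the visit. The documents nowhere mention masking, independent or duplicate reading, or automated measurement.

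**The concern.** Tp-Te depends on where the peak and the end of the T wave are placed. Grading a Valsalva phase as absent or blunted, with no numeric cut-off, is a judgement, and PRT depends on where its start and end points are set. Someone who knows that a trace is the post-titration one, and expects titration to help, may place these marks slightly differently without intending to.

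Pairing removes stable differences between subjects. It does not remove a systematic difference between how baseline and final traces are read, which goes unchanged into the mean paired difference. At stake is how far the paired tests on these measures, and the 10% benefit calls on the Valsalva measures, can be believed. Section 10 also foresees using the data set as part of a larger study, so a reading bias could be carried forward.

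**Working it through.** **The plan's own figure.** The only relevant number is n = 12. The documents give no significance level, power or SD of change, so n = 12 has no derivation to reproduce. What follows shows sensitivity; it does not estimate bias in this trial.

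**Which measures are exposed**

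| Measure (Section 5.D) | Judgement needed if read by hand | Would masked reading help? |
|---|---|---|
| Tp-Te | Yes: T-wave peak and end | Yes |
| Valsalva late phase II and phase IV | Yes: no numeric rule for the abnormal pattern | Yes |
| PRT | Yes: start and end points | Yes |
| Heart rate recovery, heart rate at fixed workload | Little, once a rule is set | Little; a preset algorithm is enough |
| Tilt and cold-pressor heart rate and blood pressure | Little, once a rule is set | Little |
| Exercise duration | Depends on effort and on staff conduct during the test | No |

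**Inputs**
- Paired t test and n = 12: Section 6.
- Two-sided 5% level: assumed.
- Reading shift b, in units of the SD of the within-subject change: assumed at 0.1, 0.25 and 0.5.
- Complete pairs: 12 is the upper limit. Section 5.B permits baseline-only participation and partial testing, and expects the neural fulcrum to be defined in 90% of patients (0.9 × 12 = 10.8). I therefore also show 10 and 8, both assumed.

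**False-positive rate of the paired test.** With no true change and shift b, the t statistic is noncentral t with n − 1 degrees of freedom and noncentrality b√n. For n = 12, √12 = 3.464, so the noncentralities are 0.1 × 3.464 = 0.346, 0.25 × 3.464 = 0.866 and 0.5 × 3.464 = 1.732. The rejection rate is P(|T| > t critical).

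| Pairs | b = 0 | b = 0.1 | b = 0.25 | b = 0.5 |
|---|---|---|---|---|
| 12 | 5.0% | 6.2% | 12.45% | 35.3% |
| 10 | 5.0% | 5.9% | 10.9% | 29.3% |
| 8 | 5.0% | 5.7% | 9.4% | 23.2% |

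A simulation of 200,000 trials at n = 12 and b = 0.25 gave 12.5%, in agreement with the exact value.

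**The 10% rule in one subject (Valsalva measures only).** If the percent change is normal with mean b and SD s, an unchanged subject passes with probability 1 − Φ((10 − b)/s). With an assumed shift of 3 percentage points:
- s = 5: from 2.3% to 8.1%
- s = 10: from 15.9% to 24.2%
- s = 20: from 30.9% to 36.3%

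Much of the chance of passing at larger s is ordinary variability, which masking would not change.

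**The case against.** The strongest reply is that the point rests on silence. The protocol does not say that traces are read by hand, or by whom. The statement that the treating team conducts the study is in the adverse-event section and does not assign that team to endpoint reading. Software may do the measuring. All of this stands, and it limits the conclusion to bias that is not prevented. If software is used, one sentence naming it and its rule would largely settle the matter.

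A reader might infer that expectation enters every before/after difference. The documents do not support that. Heart rate and blood pressure responses are numeric signals that need little judgement, exercise duration is not a trace reading, and no passage shows that a shift occurs. Nor can it be said that every benefit rule favours the expected direction, because Tp-Te has no rule. It would also be wrong to put the problem down to the missing control arm: a control arm would not reliably remove reader expectation unless the reader were also masked to arm.

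Finally, the study is exploratory and Section 6 places the t test under descriptive statistics. That lowers the stakes. It does not remove them, because the plan still tests differences and labels changes as significant clinical benefit.

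**Conclusion.** The point holds in a limited form. For Tp-Te, Valsalva late phase II, phase IV and PRT, the plan neither masks the reading to visit or device state nor fixes a measurement rule. If these are read by hand, reader expectation can enter the paired differences, and nothing in the design would remove it. The size cannot be derived from the documents. Under the assumptions above, the effect runs from negligible (about 6% false positives at a shift of 0.1 SD) to serious (35% with 12 pairs, or 23% with 8, at 0.5 SD). The consequence is weaker interpretation of exploratory physiological results, not an invalid confirmatory finding. The change is worth making because it costs little.

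**What to change.** In Sections 5.D and 10, state that:

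- Efficacy traces are stored under the study number plus a random visit code.
- After each subject's final visit, existing study staff, preferably someone who did not run that subject's tests, measure Tp-Te, the Valsalva phases and PRT in one sitting, masked to visit and device state.
- One written measurement rule or the same software is used throughout. The rule covers the ECG lead, how the T-wave end is set, and what counts numerically as a blunted phase.
- These readings are locked before the code is opened, and the Section 6 comparison uses them.
- Heart rate recovery is computed by a preset algorithm.
- Device state at each test is recorded.
- Titration and safety readings stay unmasked, so patient care is unaffected.

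The cost is relabelling work and a short delay in reading, with no extra test or visit. Because the method works on stored traces, it can also be applied to recordings already made. Stimulation artefact or staff recall may unmask some readings, and each such case should be recorded. Masking does not remove learning, regression to the mean or time effects, so the before/after results still need caution on those grounds.

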6. STATISTICAL PLAN

This is primarily an exploratory study. Descriptive statistics will be used including paired Student's T test to detect difference in cardiac physiology parameters at baseline vs. during stimulation, for the sample size of n=12. The sample size 'n' will consist of 6 females and 6 males. Each subject will be their own control.

7. RISKS AND BENEFITS

Risks associated with stimulation are addressed in the standard consent form and are considered acceptable in the opinion of the investigator.

A. RISKS

- The subject can experience coughing and hoarseness during VNS changes. If this occurs the parameters will be immediately reversed to previously tolerated parameters.
- A risk to VNS changes is a change in seizure frequency. The subject will be asked his/her seizure history at each visit and have access to the neurologist. The study neurologist will adjust the VNS parameters per routine seizure management guidelines..
- Additional risk of VNS modulation can include a decrease in heart rate and blood pressure. The parameters can be adjusted or set back to those before the study initiation and if deemed necessary, the subject will exit the study.

- Risks related to monitor pads and electrodes: Some people can have minor skin irritation or an allergic reaction from the sticky patches that are placed on the chest and limbs. The irritation should go away once the patches are removed.
- Risks related to tilt table test, valsalva maneuver or deep breathing: Some people may report feeling dizzy or lightheaded from these tests. The technician can stop the test at any time if this is reported.
- Risk related to cold pressor test: Some people may be uncomfortable with having their arm cooled for 15 minutes. The technician can adjust the temperature or stop the test if this is reported.
- Risks related to Cardiopulmonary Exercise Test (CPX): Some people may report feeling short of breath, fatigue, dizzy, or have an arrhythmia. The technician can stop the test at any time if this is reported.
- As with any use of electronic means to store data, there is a risk of breach of data security. A special code (number combination) and the patient initials will be used to identify personal health information. No personal health information about the patient, their illness, or their treatment will be made public.

B. BENEFITS

This study is not being done to immediately improve the patient's condition or health. It is aimed at acquiring scientific information regarding the heart's electrical behavior. Information obtained in this study does not have any immediate application for planning treatments for any heart condition. Patients have the right to refuse to participate in this study. There will be no personal benefit for participating in this study. However, information gained from this study helps us better understand the mechanisms of sudden cardiac death, which effects >400,000 people each year in the U.S.

8. ADVERSE EVENTS

A. DEFINITION OF ADVERSE EVENT

An adverse event (AE) is any unfavorable and unintended sign (including an abnormal laboratory finding), symptom, or disease temporally associated with the use of a medical treatment or procedure regardless of whether it is considered related to the medical treatment or procedure (attribution of unrelated, unlikely, possible, probable, or definite).

All Adverse Events (AE) will have the following assessed by the study team, as defined below:

- Diagnosis
- Event description
- Dates of onset and resolution
- Causality: assessment of relatedness to procedure
- Severity
- Outcome

B. ADVERSE EVENTS MONITORING

The patient's status will be closely monitored by the study team to assess adverse events. The study team that includes neurosurgery, neurology, and electrophysiology, will be conducting the study protocol and are the primary care team for the patient.

C. ADVERSE EVENTS

All reported AEs will be monitored by the study team until they are adequately resolved or explained.

Potential Adverse Events

Most common adverse events seen in long-term treatment with VNS (12mo and 5yrs) as reported in the literature. These symptoms were rated as mild-moderate and did not require adjustment of parameters:

- Voice alteration 55/18.7%
- Headache 16%
- Cough 15/1.5%
- Pain 15/4.7%
- Paresthesia (abnormal skin sensation) 15/1.5%
- Dyspnea 13/12.3%
- Pharyngitis 10%
- Depression 5%
- Infection 6%

Increase in seizure frequency is also a potential adverse event and will be discussed with patients during screening.

D. SERIOUS ADVERSE EVENTS

- An event that is fatal, resulting in death
- An event that is life threatening. In the opinion of the study center physician, the patient was at immediate risk of death due to the event as it occurred;
- An event that results in persistent or significant disability/incapacity;
- An event that requires inpatient hospitalization or prolongs hospitalization;
- An important medical event that, based upon appropriate medical judgment, may jeopardize the patient and may require medical or surgical intervention to prevent one of the outcomes listed above.

NOTE: Prolonged hospitalizations for a pre-existing condition is not considered a serious adverse event.

E. REPORTING SERIOUS ADVERSE EVENTS

The site investigator is responsible for ensuring that all SAEs are fully recorded and reported to the IRB per IRB reporting requirements.

9. DATA SAFETY MONITORING PLAN (DSMP)

The Principal Investigator and co-investigators will be the primary data safety monitors for this clinical trial. They will provide “real time” adverse event review and actively monitor the trial for adverse event reporting, regulatory and protocol compliance, and data accuracy. A physician group that is separate from the study will also provide Data Safety Monitoring. The group will review the protocol, study data, and safety information, such as any adverse events, twice per year. This group will include a cardiologist, a neurologist that specializes in autonomic and epilepsy, and a statistician.

The following may be reviewed:

- Annual accrual numbers and study drop-out rates. A description of any problems with recruitment or enrollment, study enrollment, and a determination as to whether the current accrual rate is sufficient to meet the intended accrual goal.
- A summary of any problems with study implementation.
- A list of all adverse events and each one’s frequency from the study population.

They may determine at any time, that the study should be modified or terminated due to patient harm and/or futility considerations.

10. DATA HANDLING

The patient will be assigned a study number after the consent is signed and the patient is enrolled. Study data will be collected and stored using the study code. Personally, identifiable data will not be collected, transmitted, or stored via the internet. A secure network server will be used to store data. A study code will link the data to the study subject. A key to the code exists. Only the study team members listed in the IRB will have access to the code.

This is a safety and feasibility study, therefore the data will be maintained for future research in the case that:

- The study team wants to use the data set to investigate any additional research questions.
- The study team uses the data set as part of a larger study in the future.

11. FINANCIAL CONSIDERATIONS

- Subjects will be not billed for any research procedures.
- Subjects will be provided a parking voucher for each research visit.
- Patients will receive a gift card for each visit completed, up to \$200 for the entire study:
 - Screening and Baseline: \$100
 - VNS Titration Visits (up to 5 visits): \$50
 - Final Visit: \$50

